5.0 Selection and Randomization of Subjects

Participants

Men and women, aged 40-75 years, presenting to an orthopaedic surgeon with a full thickness rotator cuff tear will be eligible for study screening. The inclusion and exclusion criteria are listed below.

All eligible patients will receive information about the trial verbally and in writing. After signing written informed consent, they will be randomly allocated to undergo rotator cuff repair followed by standard of care structured rehabilitation with Oxandrolone administration or standard of care structured rehabilitation with placebo. Allocation will be performed using computer software and will occur at the pharmacy to ensure that all investigators are blinded. The USC Pharmacy will prepare sequentially numbered, opaque, sealed envelope containing the assigned interventions to ensure randomness is preserved. The surgeon, PI, study team, and physical therapist will not know to which study arm the patient was randomized. The protocol for rehabilitation will remain the same for all patients. The USC Pharmacy will provide the investigators with a list of all participants and group assigned at the end of the study. Investigators will not have access to the study group assignment for any participant during data collection, to ensure adequate double-blinding of both the investigators and participants.

Inclusion criteria

- Men and women age 40-75 years old who have failed nonoperative management of chronic, full thickness rotator cuff tears confirmed by MRI without contrast

Exclusion criteria

- Patients with prior shoulder surgery or prior rotator cuff repair
- Tears larger than 5cm
- Significant glenohumeral arthritis (Hamada Grade 2 or higher)
- Untreated diabetes mellitus
- Pituitary tumor
- Rheumatoid Arthritis
- Uncontrolled hypertension
- Congestive Heart Failure
- Myocardial Infarction within the past 6 months

- End-stage renal disease
- Liver enzymes two times the normal value
- DVT within the past 6 months
- Disorder of the coagulation system
- Currently taking anticoagulation
- Claustrophobia
- Prior or current use of anabolic steroids
- Chromosomal disorders
- Prostate cancer
- Breast cancer
- Hypercalcemia
- Medications that interfere with testosterone production or function, including but not limited to 5 α -reductase inhibitors

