Females of reproductive potential must agree not to participate in the conception process (ie, active attempt to become pregnant, in vitro fertilization), and if participating in sexual activity that could lead to pregnancy, must use at least one reliable form of contraceptive. Female subjects must use contraceptives *while receiving study treatment and for 6 weeks* after stopping study treatment.

Protocol Number: APP-17-01020

Version Date: 9/1/2017

Acceptable forms of contraceptives include:

- *Condoms (male or female) with or without a spermicidal agent*
- *Diaphragm or cervical cap with spermicide*
- *Intrauterine device (IUD)*
- *Hormonal contraceptive*

NOTE: Written self-reported or partner reported sterility or lack of reproductive potential will be acceptable in place of contraceptive use.

Medical History.

A standard medical history questionnaire will be completed by the participant of past medical history of their shoulder pain, co-morbidities, and medical history of all other conditions.

Vital Signs.

Vital signs of temperature, blood pressure, respiration rate, and heart rate will be recorded.

Blood Draws

As described above, blood will be collected to monitor any adverse effects on the participant's health and to assess for medication compliance.

Outcomes:

MRI rotator cuff healing; Sugaya classification (Primary outcome). All participants will have a standardized MRI T2-weighted images without contrast, and used to classify rotator cuff integrity using 5 categories of the Sugaya classification. The 5 categories are: type I= rotator cuff sufficient thickness with homogeneously low intensity on each image; type II= rotator cuff sufficient thickness, partial high-intensity area; type III= insufficient rotator cuff thickness with less than half the thickness as compared to normal cuff, but without discontinuity; type IV= minor rotator cuff discontinuity with only 1 – 2 slices on imaging that suggest a small full-thickness tear; and type V= major discontinuity observed in more than 2 slices on imaging, suggesting a medium or large full-thickness tear.³³

MRI: Fatty infiltrate (Secondary outcome). All participants will have a standardized MRI T2-weighted images without contrast. The Goutallier grading classification⁷ will be used to assess fatty infiltration on 5 categories of grade 0= no fatty infiltration; grade 1= some fatty streaks; grade 2= less fat than muscle; grade 3= as much fat as muscle; and grade 4= more fat than muscle.

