10.0 Statistical Considerations

Statistical Methods

Descriptive statistics will be performed for participant demographics, historical information, intraoperative variables, as well as baseline testosterone, MRI measures of rotator cuff integrity, rotator cuff fatty infiltrate, rotator cuff muscle volume, shoulder strength, shoulder range of motion, patient-rated outcomes and body composition. Comparison for the primary outcome measure of rotator cuff integrity between groups from baseline to 1 year (primary endpoint) will be performed using a repeated measures analysis of Generalized Estimating Equation (GEE), appropriate for ordinal data. The GEE will also be used to compare between groups over time for the secondary outcome of fatty infiltrate (ordinal data). For all other secondary outcome variables, we will also use GEE for linear regression (ordinal data) or mixed model (continuous data) with repeatedly measured outcomes. Significance level will be established as $p < 0.05$. Analyses will be performed using STATA 13 software (College Station, TX) or SPSS and in consultation with the Statistics Department at USC.

Power Analysis and Sample Size

A power analysis for a sample size estimation was performed to detect a difference of 1 Sugaya grade (1-5 grades) classification (primary outcome) between the experimental and control group using 3 repeated measurements (baseline, 12 week, and 6 months).¹⁴ The power analysis was based with 2-sided alpha = 0.05 and power of 80%, and assuming a correlation among the repeated measures of 0.7 and overall SD of 2, giving a minimum sample size of 104 participants (n=52 participants in each group). This corresponds to an ANOVA effect size of 0.28 (28% of variance in primary outcome explained by treatment effect), or alternatively a moderate Cohen's D effect size (group mean difference divided by SD) of 0.5. Oversampling by 10% to account for possible attrition yields a total of 116 participants with 58 per group.

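### The single planning SD of 2 for the Sugaya grade cannot hold at baseline (maximum 0.5) or alongside the planned 1-grade difference after surgery (maximum 1.94); taken alone the error is conservative

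*Combined protocol and SAP*

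**What the plan says.** The power paragraph of Section 10.0 sets out to "detect a difference of 1 Sugaya grade (1-5 grades) classification (primary outcome"), "using 3 repeated measurements (baseline, 12 week, and 6 months"), with "2-sided alpha = 0.05 and power of 80"%. It does so "assuming a correlation among the repeated measures of 0.7 and overall SD of 2, giving a minimum sample size of 104 participants", or 116 after allowing for attrition. The same SD gives the standardised effect, described as a moderate Cohen's d ("group mean difference divided by SD) of 0.5"). No source is stated for the SD, and baseline is not treated differently from the later visits.

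Two other sections limit what the grades can be. The inclusion criterion in Section 5.0 admits only patients with "chronic, full thickness rotator cuff tears confirmed by MRI without contrast". Section 7.0 defines the five Sugaya types. Types I and II have sufficient thickness, and type III is thin but without discontinuity. The first type described as a full-thickness tear is "type IV= minor rotator cuff discontinuity with only 1 – 2 slices on imaging that suggest a small full-thickness tear"; type V is the larger version. Table 1 in Section 7.0 schedules the Sugaya MRI before the procedure. Section 8.0 names 6 months as the primary end-point.

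**The concern.** The SD describes a spread of grades that the eligible patients cannot show. At baseline the entry criterion confines them to two adjacent grades. After surgery an SD of 2 needs half the patients at type I, half at type V and nobody between, which forces a mean of 3. Two groups that both look like that cannot differ by the 1 grade the trial is designed to detect.

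The SD enters N, Cohen's d and the ANOVA effect size, so none of them describes this population. The power paragraph is the plan's only account of what the trial can detect. A reader of a null result would take 1 grade as the detectable limit, when the limit depends on a post-operative SD that the plan does not give.

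**Working it through.** **Inputs, all from Section 10.0:** difference 1 grade; SD 2; correlation 0.7; 3 measurements; two-sided alpha 0.05; power 80%; 52 per group.

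**1. Reproduce the plan's figure.** The SD of the mean of 3 equally correlated measurements is 2 × √((1 + 2 × 0.7)/3) = 2 × √0.8 = 1.789. The normal approximation gives 2 × (1.789 × (1.960 + 0.842))² = 50.2, so 51 per group. The repeated-measures ANOVA between-groups F test, with f = 0.5/2 = 0.25, 3 measurements and correlation 0.7, gives N = 104 exactly (power 80.6%; 79.8% at N = 102). The stated ANOVA effect size is 0.25/√0.8 = 0.28. Attrition: 104/0.9 = 115.6, which is 116 at 58 per group. SD 2 at every measurement is therefore the input that produced N.

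**2. Baseline bound.** The largest population SD on a range a to b is (b − a)/2. For grades IV and V it is (5 − 4)/2 = 0.5, a quarter of the planning value. If some baseline scans were read as type III, it would be (5 − 3)/2 = 1.0, still half of it.

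**3. Post-operative bound.** On 1 to 5 the maximum is (5 − 1)/2 = 2.0. For a group with mean m it is √((m − 1)(5 − m)):
- m = 3: √(2 × 2) = 2.0
- m = 2.5 or 3.5: √(1.5 × 2.5) = 1.94
- m = 2 or 4: √(1 × 3) = 1.73

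With means 1 grade apart, 2.5 and 3.5 is the most favourable pair, with a pooled SD of 1.94. Means of 2 and 3 give √((3 + 4)/2) = 1.87. The n − 1 divisor would allow a sample SD of 2.01 at n = 104 for the whole scale, which changes nothing of substance.

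**4. Consequence over the feasible range.** For one 6-month comparison, two-sided t test, 52 per group, 80% power, the detectable difference is 0.5547 × SD. Every SD below the 1.94 bound is an assumption; 1.41 is the value if all five types are equally likely. The last row shows the plan's value for comparison.

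| Post-operative SD | Cohen's d for 1 grade | Detectable difference (grades) | Power for 1 grade |
|---|---|---|---|
| 1.0 | 1.00 | 0.555 | >99% |
| 1.2 | 0.83 | 0.67 | 99% |
| 1.41 | 0.71 | 0.78 | 95% |
| 1.5 | 0.67 | 0.83 | 92% |
| 1.75 | 0.57 | 0.97 | 82% |
| 1.94 | 0.52 | 1.08 | 74% |
| 2 (plan) | 0.50 | 1.11 | 71% |

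Power for 1 grade is 80% or more when the SD is at most 1/0.5547 = 1.80.

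**5. The plan's own three-measurement formula.** Multiplying by √0.8 = 0.894 gives detectable differences of 0.99 (SD 2), 0.70 (1.41), 0.60 (1.2) and 0.50 (1.0). These are not interchangeable with the single-visit figures in step 4.

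**The case against.** The strongest reply is that nothing is miscalculated and the input is cautious. An SD at the top of the scale is a worst case, and too large an SD only makes the trial larger than it need be. That stands: this is a planning assumption that cannot hold, not faulty arithmetic.

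The post-operative bound is also numerically slight. Moving from 2 to 1.94 changes d from 0.50 to 0.52 and, under the plan's formula, N from 104 to 98. That stands too. A material change after surgery needs an SD well below 1.94. The background section quotes re-tear rates from up to 40% to as high as 94%, so a wide mix of healed and re-torn shoulders cannot be ruled out.

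It might also be said that the overall SD means spread pooled over visits. The plan, however, divides the group difference by it to get 0.5, and 104 reproduces only with 2 as the per-measurement SD, so that reading does not rescue it.

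A reader might infer four stronger things:
- **The trial is underpowered.** An overstated SD works the other way. Single-visit power falls below 80% only for SDs above about 1.80. Averaging in a baseline visit, where randomisation leaves no treatment effect, is a separate question and is not relied on here.
- **A 1-grade difference is wrongly called moderate.** At SDs of 1.75 to 1.94, d is 0.57 to 0.52, close to the stated 0.5. Values of 0.71 to 1.0 need an assumed SD of 1.41 or less.
- **The sponsor cannot know what the trial detects.** The documents show only an SD that is infeasible and has no stated source.
- **Enrolment could be cut.** No feasible SD is documented on which to base a cut.

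**Conclusion.** The point holds as an infeasible sample-size assumption. On the protocol's own definitions, one SD of 2 at all three visits is unattainable: at most 0.5 at baseline, and at most 1.94 within groups that differ by the planned 1 grade. The baseline contradiction is large, a factor of four; the provable post-operative excess is about 3%.

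The direction is conservative. Taken alone, the error makes N too large and d too small. Over the assumed SD range 1.0 to 1.94, the single-visit detectable difference runs from 0.555 to 1.08 grade, and d for 1 grade from 1.0 down to 0.52.

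The bounds rest only on Sections 5.0 and 7.0 and on arithmetic; the table also rests on assumed SDs, on treating the grade as a numeric score, and on comparing the groups at one visit. Six months is used because Sections 2.0 and 8.0 name it as the primary end-point for the Sugaya grade. The Statistical Methods paragraph of Section 10.0 calls 1 year the primary endpoint, which has to be reconciled separately. The same table would serve either visit with 52 per group.

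**What to change.** In the power paragraph of Section 10.0:
- Replace the SD of 2 with a post-operative Sugaya SD feasible for this population, and give its source.
- State that this SD does not apply to baseline, where eligibility confines grades to IV and V.
- Restate Cohen's d, the ANOVA effect size and the detectable difference at 52 per group. Show SDs from 1.0 up to the 1.94 bound, and label the results as a single 6-month comparison so that they are not confused with the three-measurement calculation.
- Say that power for 1 grade is at least 80% only if the SD is about 1.80 or less.
- Keep enrolment at 116.

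The cost is a few lines of text and a search for a source for the SD. No patients, visits or data collection change.

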11.0 Registration Guidelines

At time of registration, two copies of a signed and dated participant's Informed Consent form with Bill of Rights must be available (an original for patient's medical chart; one copy for the patient, one copy for the research records)

12.0 Biohazard Containment

Biohazard materials will be disposed of properly in the clinic. Blood will be stored safely and securely until analysis.

13.0 Ethical and Regulatory Considerations

All institutional and Federal regulations concerning the Informed Consent will be fulfilled. The study will be conducted in adherence to ICH Good Clinical Practice.

